3.1. Inclusion Criteria

1. Age \geq 18 years.
2. ECOG performance status of 0 or 1.
3. Adequate bone marrow function as shown by: ANC $\geq 0.5 \times 10^9/L$, Platelets $\geq 50 \times 10^9/L$, Hb ≥ 7 g/dL
4. Adequate liver function as shown by:
Total serum bilirubin ≤ 2.0 mg/dL,
ALT and AST $\leq 2.5 \times$ ULN ($\leq 5 \times$ ULN in patients with liver metastases),
Adequate renal function: serum creatinine $\leq 2.0 \times$ ULN;
5. Activating *ESR1* mutation (e.g. D538G, Y537S/N, S463P) identified on ctDNA. Novel *ESR1* alterations allowed as per discretion of PI
6. On AI with CDK4/6 inhibitor (palbociclib, ribociclib, or abemaciclib) as first line therapy for MBC for at least 12 months without evidence of clinical progression
7. Patients with histologically confirmed HR positive (ER+ and/or PR+ (>10%)), MBC

Since patients are already on AI and CDK4/6 inhibitors at the time of enrollment into the study and fulvestrant is the interventional drug, treatment can be administered as per standard of care parameters and at the discretion of treating physician

3.2. Exclusion Criteria

1. Pregnant or lactating women.
2. Received prior therapy for MBC (except for AI use for up to 4 weeks prior to initiation of CDK4/6 inhibitor).
3. Prior therapy with fulvestrant in the metastatic setting
4. HER2 positive MBC (as defined by ASCO/CAP guidelines)
5. QTc interval >480msec, Brugada syndrome or known history of QTc prolongation or Torsade de Pointes
6. Psychiatric illness, which would limit informed consent.
7. Patients who have any severe and/or uncontrolled medical conditions such as:
 - unstable angina pectoris, symptomatic congestive heart failure, myocardial infarction ≤6 months prior to enrollment, serious uncontrolled cardiac arrhythmia, or any other clinically significant cardiac disease
 - active (acute or chronic) or uncontrolled severe infection, liver disease such as cirrhosis, decompensated liver disease, and active and chronic hepatitis (i.e. quantifiable HBV-DNA and/or positive HbsAg, quantifiable HCV-RNA),
 - severe hepatic impairment (Child-Pugh C)
8. HIV-positive patients on combination antiretroviral therapy
9. Expected survival < 6 months
10. Any serious medical illness, other than that treated by this study, which would limit survival to less than 1 month
11. Patients with a history of non-compliance to medical regimens or who are considered potentially unreliable or will not be able to complete the entire study;
12. Patients who are currently part of or have participated in any clinical investigation with an investigational drug within 1 month prior to dosing;
13. Women of child-bearing potential (WOCBP), defined as all women physiologically capable of becoming pregnant, must use highly effective methods of contraception during the study and 8 weeks after the end of treatment. Highly effective contraception methods include combination of any two of the following:
 - Placement of an intrauterine device (IUD) or intrauterine system (IUS);
 - Barrier methods of contraception: condom or occlusive cap (diaphragm or cervical/vault caps) with spermicidal foam/gel/film/cream/ vaginal suppository;
 - Total abstinence or;
 - Male/female sterilization.
14. Male patients whose sexual partner(s) are WOCBP who are not willing to use adequate contraception, during the study and for 8 weeks after the end of treatment

4. REGISTRATION

4.1. Patient identification/Enrollment

HR positive (ER >10%) MBC patients who are on AI with CDK4/6 inhibitor (palbociclib, ribociclib, or abemaciclib) as first line therapy for at least 12 months would be screened for ctDNA analysis. Patients with positive *ESR1* mutations identified on ctDNA would be randomized to fulvestrant versus continuation of AI that they started on.

Patients must meet all of the eligibility requirements listed in Section 3.

4.2. Instructions for patients who do not start assigned protocol treatment

If a patient does not receive any assigned protocol treatment, baseline and follow-up data will still be collected. Document the reason for not starting protocol treatment on one of the baseline forms. Also report the date and type of the first non-protocol treatment that the patient receives.

5. TREATMENT PLAN

5.1. Treatment

- **Fulvestrant** 500 mg should be administered intramuscularly (+/- 3 days) into the buttocks slowly (1 - 2 minutes per injection) as two 5 mL injections, one in each buttock, on days 1, 15 of Cycle 1 and then Day 1 of Cycles 2 and beyond (Cycle = 28 days).
- **Ribociclib** tablets should be taken orally in combination with NSAI (non-steroidal aromatase inhibitor) or fulvestrant. Starting dose – 600 mg orally taken once daily for 21 consecutive days followed by 7 days off treatment.
- **Palbociclib** capsules should be taken orally with food in combination with an NSAI or fulvestrant. Starting dose – 125 mg orally taken once daily for 21 consecutive days followed by 7 days off treatment.
- **Abemaciclib** tablets should be taken orally in combination with NSAI or fulvestrant. Starting dose – 150 mg twice daily
- **Letrozole** 2.5 mg or **anastrozole** 1 mg orally should be taken orally daily
- Pre/Peri-menopausal women treated with CDKI plus NSAI or fulvestrant therapy should be treated with luteinizing hormone-releasing hormone (LHRH) agonists according to current clinical practice standards.

Since treatment involves standard of care agents, patients can pursue treatment outside of MD Anderson, under the supervision of the local oncologist. However, clinical documents to confirm administration should be sent for review. Additionally, clinical assessments to confirm response (e.g. staging scans) should be performed at MD Anderson.

5.2. Drug Monitoring and Dose Modifications

Administration of palbociclib, ribociclib, or abemaciclib should follow standard procedure as outlined in the package insert. Dose interruption, modification or discontinuation based on individual safety and tolerability can be carried out as per investigator's or treating physician's discretion.

Palbociclib

The palbociclib prescribing information recommends monitoring complete blood counts prior to starting therapy and at the beginning of each cycle, as well as on day 15 of the first 2 cycles.

Based on pharmacokinetic analysis from prior studies, mild hepatic impairment had no effect on the exposure of palbociclib (bilirubin \leq ULN and AST $>$ ULN, or total bilirubin >1.0 to $1.5 \times$ ULN and any AST). The pharmacokinetics of palbociclib have not been studied in patients with moderate or severe hepatic impairment (total bilirubin $>1.5 \times$ ULN and any AST).

Based on pharmacokinetic analysis, mild (CrCl 60-90 ml/min) or moderate renal dysfunction (CrCl 30-60 ml/min) had no effect on the exposure of palbociclib. The pharmacokinetics of palbociclib have not been studied in patients with moderate or severe renal dysfunction.

Most common adverse reactions (incidence $\geq 10\%$) with palbociclib were neutropenia, infections, leukopenia, fatigue, nausea, stomatitis, anemia, alopecia, diarrhea, thrombocytopenia, rash, vomiting, decreased appetite, asthenia, and pyrexia.

Table-2: Recommended Dose Modification for Palbociclib

Dose Level	Dose
Starting dose	125 mg/day
First dose reduction	100 mg/day
Second dose reduction	75 mg/day
Third dose reduction	75 mg/day*

*Two weeks on, two weeks off. If further dose reduction is required, discontinue palbociclib

Ribociclib

The ribociclib prescribing information recommends monitoring complete blood counts and liver function tests (LFTs) prior to starting therapy and at the beginning of each subsequent 4 cycles and as clinically indicated, as well as on day 15 of the first 2 cycles. Additionally, EKGs prior to initiating therapy, Day 14 of first cycle, and the beginning of second cycle are required. Electrolytes at the beginning of each cycle for 6 cycles are also recommended.

No dose adjustment is necessary in patients with mild hepatic impairment (Child-Pugh class A). The recommended starting dose is 400 mg once daily for patients with moderate (Child-Pugh class B) and severe hepatic impairment (Child-Pugh class C)

Ribociclib should be avoided in patients who are at risk of developing QTc prolongation (e.g. long QT syndrome, electrolyte abnormalities, unstable angina or arrhythmias)

Most common adverse reactions (incidence $\geq 20\%$) are neutropenia, nausea, fatigue, diarrhea, leukopenia, alopecia, vomiting, constipation, headache and back pain.

Table-3: Recommended Dose Modification for Ribociclib

Dose Level	Dose
Starting dose	600 mg/day
First dose reduction	400 mg/day
Second dose reduction	200 mg/day*

*If further dose reduction below 200 mg/day is required, treatment should be discontinued

Abemaciclib

The abemaciclib prescribing information recommends monitoring complete blood counts and liver function tests (LFTs) prior to starting therapy, every 2 weeks for the first 2 months, monthly for the next 2 months, and as clinically indicated.

No dosage adjustments are necessary in patients with mild or moderate hepatic impairment (Child-Pugh A or B). The recommended starting dose for patients with severe hepatic impairment (Child Pugh-C) is 150 mg daily.

Abemaciclib can increase serum creatinine due to inhibition of renal tubular secretion transporters, without any effect on glomerular function. Typical elevations happen during the first cycle, but they remained stable through the treatment period and were reversible with discontinuation. No dosage adjustment is recommended for patients with mild or moderate renal impairment ($\text{CrCl} \geq 30-89 \text{ mL/min}$). The

pharmacokinetics of abemaciclib has in patients with severe renal impairment ($\text{CrCl} < 30 \text{ mL/min}$), dialysis, or end stage renal disease is unknown.

Most common adverse reactions (incidence $\geq 20\%$) were diarrhea, neutropenia, nausea, abdominal pain, infections, fatigue, anemia, leukopenia, decreased appetite, vomiting, headache, alopecia, and thrombocytopenia

Table-4: Recommended Dose Modification for Abemaciclib	
Dose Level	Dose
Starting dose	150 mg twice daily
First dose reduction	100 mg twice daily
Second dose reduction	50 mg twice daily

Fulvestrant

Fulvestrant is administered intramuscularly 500 mg on days 1, 15 of Cycle 1, and once monthly thereafter (Cycle = 28 days). For patients with moderate hepatic impairment, fulvestrant should be administered at 250 mg on days 1, 15 and once monthly thereafter. Moderate hepatic impairment is defined as Child-Pugh class B

The most common, clinically significant adverse reactions, occurring in $\geq 5\%$ of patients receiving fulvestrant are, pain at the site of injection, nausea/vomiting, bone pain, arthralgia, headache, fatigue, hot flashes, anorexia, asthenia, musculoskeletal pain, cough, dyspnea, and constipation. Increase in hepatic enzymes (transaminases and alkaline phosphates) were observed in more than 15% of patients, and was independent of the dose.

For detailed information on dose modification for fulvestrant see Packaging Insert.

5.3. Concomitant Therapy

Patients must be instructed not to take any medications (over-the-counter or other products) during the protocol treatment period without prior consultation with the investigator. All medications (other than study drug) taken within 28 days of starting study treatment through the 30-day safety follow up visit should be reported on the CRF.

All supportive measures consistent with optimal patient care should be given throughout the study. Exceptions include the use of growth factors to treat anemia or thrombocytopenia as such use has been associated with decreased survival and increased thrombotic events in patients with breast cancer. The use of myeloid growth factors in the form of G-CSF should follow ASCO guidelines. G-CSF can be administered to treat CDK inhibitor-induced neutropenia as determined by the treating physician.

Dose Modifications for Use with Strong CYP3A Inhibitors

Concomitant use of strong CYP3A inhibitors should be avoided with **palbociclib**. If patients must be co-administered with a strong CYP3A inhibitor, dose of Palbociclib should be reduced to 75 mg daily. Avoid concurrent use of palbociclib with strong CYP3A inducers. The dose of sensitive CYP3A4 substrates with narrow therapeutic indices may need to be reduced when given concurrently with palbociclib.

Concomitant use of strong CYP3A inhibitors should be avoided with **ribociclib**. If patients must be co-administered with a strong CYP3A inhibitor, dose of ribociclib should be reduced to 400 mg daily. Avoid

concomitant use of ribociclib with strong CYP3A inducers. The dose of sensitive CYP3A4 substrates with narrow therapeutic indices may need to be reduced when given concurrently with ribociclib.

Concomitant use of ketoconazole should be avoided with **abemaciclib**. If patients must the co-administered with a strong CYP3A inhibitor, dose of abemaciclib should be reduced to 100 mg twice daily. Avoid concomitant use of abemaciclib with strong CYP3A inducers.

Patients should avoid pomegranates or pomegranate juice, grapefruit, all of which are known to inhibit cytochrome CYP3A enzymes and may increase the exposure to palbociclib and ribociclib.

Avoid concomitant use of drugs known to prolong QT interval such as antiarrhythmics (including, but not limited to amiodarone, disopyramide, procainamide, quinidine and sotalol), and other drugs known to prolong the QT interval (including, but not limited to, chloroquine, halofantrine, clarithromycin, haloperidol, methadone, moxifloxacin, bepridil, pimozide and ondansetron).

There are no known drug-drug interactions with **fulvestrant**

Cytochrome P450 inhibitors/inducers/substrates

A list of drugs that are strong inducers or inhibitors of CYP3A4 and sensitive substrates of CYP3A4 with a narrow therapeutic window is provided here:

CYP enzymes	Strong inhibitor	Strong inducer	Sensitive substrate	Substrate with narrow therapeutic range
CYP3A4	Boceprevir, clarithromycin, conivaptan, grapefruit juice, indinavir, itraconazole, ketoconazole, lopinavir/ritonavir, mibepradil, nefazodone, neflifavir, posaconazole, ritonavir, saquinavir, telaprevir, telithromycin, voriconazole	Avasimibe, carbamazepine, phenytoin, rifampin, St. John's wort	Alfentanil, aprepitant, budesonide, buspirone, conivaptan, darifenacin, darunavir, dasatinib, dronedarone, eletriptan, eplerenone, everolimus, felodipine, indinavir, fluticasone, lopinavir, lovastatin, lurasidone, maraviroc, midazolam, nisoldipine, quetiapine, saquinavir, sildenafil, simvastatin, sirolimus, tolvaptan, tipranavir, triazolam, ticagrelor, vardenafil	Alfentanil, astemizole, cisapride, cyclosporine, dihydroergotamine, ergotamine, fentanyl, pimozide, quinidine, sirolimus, tacrolimus, terfenadine

5.4. Adverse Events

Information about common side effects are already known about the agents (palbociclib, ribociclib, abemaciclib, letrozole, anastrozole, fulvestrant).

An adverse event (AE) is the appearance or worsening of any undesirable sign, symptom, or medical condition occurring after starting the study drug even if the event is not considered to be related to study

drug. Medical conditions/diseases present before starting study drug are only considered adverse events if they worsen after starting study drug. Abnormal laboratory values or test results constitute adverse events only if they induce clinical signs or symptoms, are considered clinically significant, or require therapy.

Adverse events (including lab abnormalities that constitute AEs) should be described using a diagnosis whenever possible, rather than individual underlying signs and symptoms. When a clear diagnosis cannot be identified, each sign or symptom should be reported as a separate AE.

As far as possible, each adverse event should be evaluated to determine:

1. The severity grade (CTCAE Grade 1-4).
2. Its duration (Start and end dates or if continuing at the Safety Follow-up Visit).
3. Its relationship to the study treatment (Reasonable possibility that AE is related: No, Yes).
4. Action taken with respect to study or investigational treatment (none, dose adjusted, temporarily interrupted, permanently discontinued, hospitalized, unknown, not applicable).
5. Whether medication or therapy was given (no concomitant medication/non-drug therapy, concomitant medication/non-drug therapy).
6. Outcome (not recovered/not resolved, recovered/resolved, recovering/resolving, recovered/resolved with sequelae, fatal, unknown).
7. Whether it is serious, where a serious adverse event (SAE) is defined as in the Serious Adverse Events subsection.

All adverse events should be treated appropriately. Such treatment may include changes in study drug treatment including possible interruption or discontinuation, starting or stopping concomitant treatments, changes in the frequency or nature of assessments, hospitalization, or any other medically required intervention. Once an adverse event is detected, it should be followed until its resolution, and assessment should be made at each visit (or more frequently, if necessary) of any changes in severity, the suspected relationship to the study drug, the interventions required to treat it, and the outcome.

The investigator (or physician designee) is responsible for verifying and providing source documentation for all adverse events and assigning the attribution for all adverse events for subjects enrolled.

Protocol #2018-0287 will be monitored by the MD Anderson External Data and Safety Monitoring Board (EDSMB).

Laboratory test abnormalities

Laboratory abnormalities that constitute an adverse event in their own right (are considered clinically significant, induce clinical signs or symptoms, require concomitant therapy or require changes in study treatment), should be recorded on the Adverse Events CRF. Whenever possible, a diagnosis, rather than a symptom should be provided (e.g. anemia instead of low hemoglobin). Laboratory abnormalities that meet the criteria for Adverse Events should be followed until they have returned to normal or an adequate explanation of the abnormality is found. Laboratory abnormalities, that do not meet the definition of an adverse event, should not be reported as adverse events. A Grade 3 or 4 event (severe) as per CTCAE does not automatically indicate a SAE unless it meets the definition of serious as defined below and/or as per investigator's discretion. Grade 3 or 4 neutropenia is an expected, on-target, AE with CDK4/6 inhibitors. Thus, dose modifications for neutropenia should follow specific prescribing information brochure guidelines.

Recommended Adverse Event Recording Guidelines

Attribution	Grade 1	Grade 2	Grade 3	Grade 4	Grade 5
Unrelated	Phase I				

		Phase II		Phase II	
				Phase III	Phase III
Unlikely	Phase I	Phase I	Phase I	Phase I	Phase I
			Phase II	Phase II	Phase II
				Phase III	Phase III
Possible	Phase I	Phase I	Phase I	Phase I	Phase I
	Phase II	Phase II	Phase II	Phase II	Phase II
		Phase III	Phase III	Phase III	Phase III
Probable	Phase I	Phase I	Phase I	Phase I	Phase I
	Phase II	Phase II	Phase II	Phase II	Phase II
		Phase III	Phase III	Phase III	Phase III
Definitive	Phase I	Phase I	Phase I	Phase I	Phase I
	Phase II	Phase II	Phase II	Phase II	Phase II
		Phase III	Phase III	Phase III	Phase III

Pregnancy

Based on animal studies, palbociclib, ribociclib, or abemaciclib can cause fetal harm when administered to pregnant women. In animal reproduction studies, administration of palbociclib during organogenesis resulted in embryo-fetal toxicity at maternal exposures that were ≥ 4 times the human clinical exposure based on area under the curve (AUC). In animal reproduction studies, administration of ribociclib to pregnant rats and rabbits during organogenesis caused embryo-fetal toxicities at maternal exposures that were 0.6 and 1.5 times the human clinical exposure, respectively, based on area under the curve (AUC). In animal reproduction studies, administration of abemaciclib during organogenesis was teratogenic and caused decreased fetal weight at maternal exposures similar to human clinical exposure based on AUC at the maximum recommended human dose. Pregnant women should be advised of potential risk to fetus and should use effective contraception during and for at least 4 weeks after the last dose of palbociclib, ribociclib, or abemaciclib.

Lactation

There is no information regarding the presence of palbociclib, ribociclib, or abemaciclib in human milk, their effects on milk production or the breast fed infant. Because of the potential for serious adverse effects in breast fed infants with palbociclib, ribociclib, or abemaciclib, lactating women should not breast feed during treatment and for 3 weeks after the last dose.

Serious Adverse Event (SAE) Reporting

An adverse event or suspected adverse reaction is considered “serious” if, in the view of either the investigator or the Western Institutional Review Board (WIRB), it results in any of the following outcomes:

- Death
- A life-threatening adverse drug experience – any adverse experience that places the patient, in the view of the initial reporter, at immediate risk of death from the adverse experience as it occurred. It does not include an adverse experience that, had it occurred in a more severe form, might have caused death.
- Inpatient hospitalization or prolongation of existing hospitalization
- A persistent or significant incapacity or substantial disruption of the ability to conduct normal life functions.
- A congenital anomaly/birth defect.

Important medical events that may not result in death, be life-threatening, or require hospitalization may be considered a serious adverse drug experience when, based upon appropriate medical judgment, they may jeopardize the patient or subject and may require medical or surgical intervention to prevent one of

the outcomes listed in this definition. Examples of such medical events include allergic bronchospasm requiring intensive treatment in an emergency room or at home, blood dyscrasias or convulsions that do not result in inpatient hospitalization, or the development of drug dependency or drug abuse (21 CFR 312.32).

- Important medical events as defined above, may also be considered serious adverse events. Any important medical event can and should be reported as an SAE if deemed appropriate by the Principal Investigator.
- All life-threatening or fatal events, that are unexpected, and related to the study drug, must have a written report submitted within 24 hours (next working day) of knowledge of the event to the WIRB.
- All events occurring during the conduct of a protocol and meeting the definition of a SAE must be reported to the WIRB in accordance with the timeframes and procedures outlined in the WIRB reporting requirements using the WIRB "Promptly Reportable Information" form to report the following information to within 5 days:
 1. New or increased risk
 2. Protocol deviation that harmed a subject or placed subject at risk of harm
 3. Protocol deviation made without prior IRB approval to eliminate an immediate hazard to a subject
 4. Audit, inspection, or inquiry by a federal agency
 5. Written reports of federal agencies (e.g., FDA Form 483)
 6. Allegation of Noncompliance or Finding of Noncompliance
 7. Breach of confidentiality
 8. Unresolved subject complaint
 9. Suspension or premature termination by the sponsor, investigator, or institution
 10. Incarceration of a subject in a research study not approved to involve prisoners
 11. Adverse events or IND safety reports that require a change to the protocol or consent
 12. State medical board actions
 13. Unanticipated adverse device effect
 14. Information where the sponsor requires prompt reporting to the IRB Information not listed above does not require prompt reporting to WIRB

Information not listed above does not require prompt reporting to WIRB. Please note, consistent with AAHRPP's requirements in connection with its accreditation of IRBs, the individual and/or organization submitting research for review shall promptly communicate or provide, and where necessary cause each investigator to promptly communicate or provide, the following information relevant to the protection of human subjects to WIRB in a timely manner:

- a. Upon request of the IRB, a copy of the written plan between sponsor or CRO and site that addresses whether expenses for medical care incurred by human subject research subjects who experience research related injury will be reimbursed, and if so, who is responsible in order to determine consistency with the language in the consent document.
- b. Any site monitoring report that directly and materially affects subject safety or their willingness to continue participation. Such reports will be provided to the IRB within 5 days.
- c. Reports from any data monitoring committee, data and safety monitoring board, or data and safety monitoring committee in accordance with the time frame specified in the research protocol.
- d. Any findings from closed research when those findings materially affect the safety and medical care of past subjects. Findings will be reported for 2 years after the closure of the research.

- Serious adverse events will be captured from the time of the first protocol-specific intervention, until 30 days after the last dose of drug, unless the participant withdraws consent. Serious adverse events must be followed until clinical recovery is complete and laboratory tests have returned to baseline, progression of the event has stabilized, or there has been acceptable resolution of the event.

Reporting to FDA:

It is the responsibility of the PI and the research team to ensure serious adverse events are reported according to the Code of Federal Regulations, Good Clinical Practices, the protocol guidelines and Western Institutional Review Board policy.

The Guardant 360 Assay is a liquid- based biopsy test with clinically minimal risks.

Device Failure

It is the responsibility of the PI and the research team to ensure unanticipated adverse device effects are reported according to the Code of Federal Regulations, Good Clinical Practices, the protocol guidelines and Western Institutional Review Board policy.

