9. STATISTICAL CONSIDERATIONS

Primary/Secondary Objectives:

This is a randomized, open-label, Phase II, for HR positive advanced breast cancer patients who have been treated with AI and CDK as first line in the metastatic setting for at least 12 months and who have *ESR1* mutations identified through ctDNA assay.

[name], MS, Department of Biostatistics at MD Anderson Cancer Center, will oversee the implementation of the statistical analysis. The primary endpoint is PFS, which is measured from the date of study randomization to the date of event (ie, death and/or disease progression) or the date of last follow-up if no event has occurred. Survival curves for PFS will be analyzed using the Kaplan-Meier method and survival difference across groups will be examined by log rank test. Patients alive and disease-free at the latest clinical evaluation will be censored for PFS at the date of that evaluation. We will estimate the treatment comparison with 95% confidence intervals and p-value using Cox proportional hazards regression and we will assess the proportional hazard assumption using graphs of rescaled Schoenfeld residuals and related tests. We would attempt to identify independent predictors of PFS using multivariable Cox PH regression analysis. Analysis for OS and PFS from the start of next line of therapy will be performed as described for PFS from the date of randomization. Randomization will be performed using Core. Stratification factors include recurrence free interval (\leq 3 years vs. $>$ 3 years), prior adjuvant endocrine therapy (tamoxifen vs. aromatase inhibitor), and site of metastasis (bone vs. visceral).

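### The recommended adverse event table makes Phase II recording of Grade 1-2 events depend on attribution by an investigator who knows the arm, which conflicts with the protocol's own adverse event definition and may distort descriptive low-grade safety data

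*Combined protocol and SAP*

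**What the plan says.** - Section 9 describes the design: "This is a randomized, open-label, Phase II, for HR positive advanced breast cancer patients". The Phase II entries of the recording table therefore apply, and attribution is made with knowledge of the arm.
- Section 5.4 gives the table under the heading "Recommended Adverse Event Recording Guidelines". It crosses five attribution levels with five grades and names the trial phases for which recording is recommended.
- Section 5.4 makes the investigator or physician designee responsible for "assigning the attribution for all adverse events for subjects enrolled". No blinded or independent attribution is described.
- Earlier in Section 5.4, an adverse event is one "occurring after starting the study drug even if the event is not considered to be related". As far as possible, each is to be evaluated on several items, including "Its relationship to the study treatment (Reasonable possibility that AE is related: No, Yes".
- Section 5.4 also says: "Medical conditions/diseases present before starting study drug are only considered adverse events if they worsen after starting study drug".
- Section 3.1 states that "fulvestrant is the interventional drug" and requires at least 12 months on an AI with a CDK4/6 inhibitor at entry. A footnote to Appendix 1 says that controls stay on the treatment they were already taking.

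**The concern.** An adverse event definition that ignores relatedness is meant to keep causal judgement out of data capture. The table brings that judgement back for low grades, in a trial where the person judging knows the treatment. The arms also differ in a way that could influence the judgement: one group has just begun a new drug, and the other has taken the same regimen for a year or more. The same mild new symptom could be rated possible in the first group and unlikely in the second, and only the first rating leads to recording under the table.

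At stake is the description of low-grade tolerability. Patients enter without clinical progression, so the tolerability of an early switch matters when its value is judged. A by-arm table of Grade 1-2 events could show a difference that reflects recording rather than occurrence.

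**Working it through.** The plan states no figure on this point, so the check is mainly a comparison of texts.

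**1. The table, Phase II entries only (Section 5.4)**

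| Attribution | Grades with a Phase II entry |
|---|---|
| Unrelated | Row broken in the text available; as read, Phase II falls under Grades 2 and 4, which is not a reliable reading |
| Unlikely | 3, 4, 5 |
| Possible | 1 to 5 |
| Probable | 1 to 5 |
| Definitive | 1 to 5 |

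The last four rows are intact. At Grades 1-2, moving a rating from unlikely to possible changes the recommendation from not recording to recording. At Grades 3-5 the same move changes nothing.

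**2. The table against the rest of Section 5.4**

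- The definition covers unrelated events. The table leaves out unlikely events at Grades 1-2.
- A sign or symptom without a clear diagnosis is to be reported as an adverse event of its own, and qualifying laboratory abnormalities go on the adverse event CRF. Neither instruction carries an attribution condition.
- The evaluation item has two levels and the table has five. Section 5.4 does not say how No/Yes maps to unlikely and possible, so the No/Yes item alone does not fix which row of the table applies.

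**3. Where the arms could differ (Sections 5.1 and 5.2)**

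Section 5.1 provides for a CDK4/6 inhibitor with either endocrine partner. Fatigue and nausea are listed for all three CDK4/6 inhibitors, and headache for ribociclib and abemaciclib. A rating of possible is therefore available for these in either arm. Arthralgia, hot flashes, bone pain and musculoskeletal pain are listed for fulvestrant and for none of the CDK4/6 inhibitors. Section 5.2 has no reaction list for letrozole or anastrozole. For this second group of symptoms, the protocol supplies a listed cause in the fulvestrant arm and none in the control arm.

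**4. Size and direction**

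Let p be the true proportion with a given Grade 1-2 symptom, equal in both arms. Let aF and aC be the shares rated possible or higher on fulvestrant and control. If the table is followed, and unrelated Grade 1-2 events are also left out (an assumption, since that row is unreadable), then:

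recorded difference = p × (aF − aC)

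The documents give none of the three values. With assumed values, only to show that the sign is open:

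- p = 0.40, aF = 0.90, aC = 0.70: 0.36 − 0.28 = +0.08
- p = 0.40, aF = aC = 0.90: 0.36 − 0.36 = 0
- p = 0.40, aF = 0.70, aC = 0.90: 0.28 − 0.36 = −0.08

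The rule permits an artefact, but the documents do not fix its size or sign.

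**The case against.** The strongest reply is that the table is only a recommendation, while the text around it leans towards capture regardless of cause. On that view, low-grade events rated unlikely may well be recorded, and the filter may never operate. This stands in part. A reader might infer that Grade 1-2 events are recorded solely when rated possible or higher, but the word Recommended, the unconditional definition and the unreadable row for unrelated events do not support so absolute a rule. What remains is two instructions that disagree, with nothing to say which governs.

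Other stronger readings also fail:

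- *Low-grade toxicity will be over-recorded on fulvestrant.* Nothing in the documents says that attribution will differ by arm. Section 5.4 treats the side effects of the AIs as already known, so an investigator may rate control events possible without a list. The reaction lists in Section 5.2 also use different incidence cut-offs (5% for fulvestrant, 10% or 20% for the CDK4/6 inhibitors), which in itself makes the fulvestrant list more inclusive.
- *Any asymmetry comes from the table.* The separate rule on pre-existing conditions could also lower counts for patients on a long-standing regimen.
- *The events are lost for good.* Section 5.4 requires source documentation for all adverse events, so events missing from the CRF should be traceable.
- *The monitoring board will be shown the distorted comparison.* Section 5.4 says only that an external board monitors the protocol. It does not describe by-arm adverse event tables.

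It is also fair to say that Section 2 has no safety objective or endpoint and Section 9 plans no between-arm adverse event comparison. That limits the consequence. It does not protect a descriptive by-arm table, should one be produced.

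**Conclusion.** The point holds as a minor improvement. In the readable rows, recommended Phase II recording of Grade 1-2 events turns on whether an arm-aware investigator chooses unlikely or possible, and this conflicts with the definition and the two-level relatedness item in the same section. Low-grade events listed for fulvestrant but for none of the CDK4/6 inhibitors may be recorded more fully in the fulvestrant arm.

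That direction is an inference. It assumes that sites follow the table and that newly started treatment attracts more attribution than continued treatment. No magnitude can be given. The effect is confined to descriptive Grade 1-2 safety data; the PFS analysis, power, alpha and the interim rule do not depend on it.

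**What to change.** Reconcile the table with the definition in Section 5.4. Record adverse events on the CRF in both arms by the same rule, regardless of attribution, and keep attribution as a descriptive field. Choose one relatedness scale, either No/Yes or five levels, and use it throughout. The cost is more low-grade adverse event entries. No change to the design, the sample size or the efficacy analysis is needed.

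This does not remove any asymmetry from the rule on pre-existing conditions, which should be kept in mind when low-grade events are described by arm.

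Limiting between-arm descriptions to Grade 3 or higher events of any attribution would avoid the extra entries. It should not be relied on unless the sponsor confirms that the Unrelated row of the source table covers Grades 3 to 5 for Phase II. It would also restrict a comparison that the plan does not currently propose.
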